These are detections that could not be classified as a an obviously false positive at first sight and which is indicated by the endoscopists as a side that needs further inspection. In case this is not spotted by the endoscopists, the second observer will ask the endoscopists to perform a second or close-by inspection for better evaluation, not showing endoscopic evidence of a polyp

We subdivided this type of false positive detections in 3 subdivisions:

- 1) (Thickened) fold
- 2) Other: mucosal lesions different from normal colonic mucosa
- 3) Not relocated: the detection could not be relocated for additional endoscopic inspection
- (3) Other false positive detections

This is every other false positive detection that does not fit any other class and does not need a second or close-by inspection.

 True positive detection: The AI-tool detects a mucosal lesion that is endoscopically diagnosed to be a polyp at first sight (detected by the endoscopist) or after second and close-by look (if initially missed by the endoscopist).

If in case of doubt the endoscopist takes a biopsy to rule out a polyp, this detection will be considered as a true positive detection by AI.

Negative detections:

- False negative detection: Every polyp that is found by the endoscopist and is not detected by the AI tool before the attempt of endoscopic optical diagnosis. On detection of a polyp, the endoscopist will use a standardized verbal action (ask "Did the system detect the polyp as well?"), to inform the second observer about the detection. Immediately the second observer hits the detection button on the AI system. This is a button that initiates timelimited indicator on the AI coupled screen for 1 second. If no detection is made by the AI system during that time, the endoscopically found polyp is to be considered as a false negative detection for the AI system.

5. Endpoints

Primary endpoint

Total polyp detection during single pass colonoscopy by the artificial intelligence tool in comparison to polyp detection by the endoscopist with endoscopic diagnosis as a gold standard.

Secondary endpoints

- 1. Total polyp detection during single pass colonoscopy by the artificial intelligence tool in comparison to polyp detection by the endoscopist with histological diagnosis as a gold standard.
- 2. The number of extra detected polyps by artificial intelligence with the endoscopic diagnosis as a gold standard.

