- 3. The number of extra detected polyps by artificial intelligence with the histological diagnosis as a gold standard.
- 4. The endoscopist's polyp miss rate defined as the additional detection of polyps during colonoscopy
- 5. The false positive rate during clean withdrawal.

Exploratory endpoints

- 1. Correlation between the Boston Bowel Preparation Score and the number of false positive detections during colonoscopy.
- 2. Correlation between the endoscopist's historical adenoma detection rate and the number of extra detections and false negative detections by the artificial intelligence system.
- 3. Correlation between the polyp size and number of false negatives and additional detections.
- 4. Correlation between the Paris classification and the number of false negatives and additional detections.

- 5. Correlation between the total number of polyps per colonoscopy and additional detections.
- 6. Correlation between the experience of the endoscopist and additional detections.

6. Study Design

This is an investigator-initiated multicentre non-randomized prospective interventional trial to validate the performance of a novel state-of-the-art computer-aided diagnostic (CAD) tool in polyp detection implemented as second observer during routine diagnostic colonoscopy and to evaluate its feasibility in daily endoscopy. Consecutive patients referred for a screening, surveillance or diagnostic colonoscopy will be included. After standard bowel preparation with PEG based solutions, patients will undergo a standard colonoscopy performed by an endoscopist with moderate to high adenoma detection rate (ADR > 20% and < 50%). A second observer, who is not a trained endoscopist, but a person trained for recognition of polyps and endoscopic lesions (see section 8), will follow the procedure on a bedside AI-tool to count the number of detections made by the AI system and categorize the results into positive or negative results as follows (1) true positive, (2) false negative or (3) false positive (detailed description, see section 4).

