Exclusion criteria for study analysis

- Colonic inflammation of > 30cm during colonoscopy
- Incomplete colonoscopy for any reason
- Incomplete recording or technical failure of the artificial intelligence system

8. Study Procedures

Bowel preparation

Before endoscopy patients will be prepared either at home either in hospital with standard bowel preparation according to local practice in the respective research centers, with an oral polyethylene glycol based regimen and if necessary, with an additional water enema. During endoscopy, all residual stools will be removed from the colonic wall by rinsing with water with or without dimeticon. Every subject's bowel preparation will be scored using the Boston Bowel Preparation Scale (BBPS).

Endoscopy, video recording

Endoscopy will be performed in patients on the scheduled appointment as initially made after selection based on referral. Video recording of the procedure will be initiated to record the patient's number upon the case report form before the endoscope is introduced in the anal canal. Before withdrawal, a picture of the caecum needs to be taken. During withdrawal the bowel should be as maximal inflated as possible for a high-quality inspection. A single pass withdrawal will be applied during inspection.

If a polyp is found, it can be resected after an endoscopist's optical assessment. This endoscopist's optical assessment should include description of the polyp size, location, Paris classification and if possible endoscopic diagnosis of most probable histology (hyperplastic, sessile serrated, adenoma or carcinoma).

If more than 5 polyps with apparent hyperplastic morphology are found in the rectosigmoid, the first 5 polyps will be included for analysis of the AI tool performance and will be resected for histological assessment and inclusion in the study. Any additional apparent hyperplastic polyps in the rectosigmoid exceeding the number of 5 will be discarded from the study for practical reasons. Most of these polyps will be hyperplastic and are clinically irrelevant. Additional separate biopsies of these sometimes many polyps will incur unnecessary costs. The entire procedure needs to be recorded as one video.

Second observer

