- All SAEs must be followed up until the outcome of the event is 'recovered', 'recovered with sequelae', 'not recovered' (in case of death due to another cause) or 'death' (due to the SAE) and until all related queries have been resolved, or until end of trial (whichever occurs first).
- Non-serious AEs must be followed up until the patient's last study visit, and until all related queries have been resolved.

Pregnancy

Female subjects must be instructed to notify the Investigator immediately if they become pregnant during the trial. The Investigator must report any pregnancy in subjects during the trial to the Sponsor.

Death

All deaths will be reported without delay to the Sponsor (irrespective of whether the death is related to disease progression, study procedure or is an unrelated event). The sponsor will notify all deaths, as soon as possible after becoming aware, to the Central EC and the EC of the concerned site and provide additional information if requested.

Reporting requirements to Ethics Committee's (EC's) The Investigator is responsible for ensuring that all safety events are recorded in the (e)CRF and reported to the Sponsor in accordance with instructions provided below.

The Sponsor will promptly evaluate all SAEs and AESIs against medical experience to identify and expeditiously communicate possible new safety findings to Investigators and based on applicable legislation.

Annual reporting

The sponsor has the obligation to, once a year throughout the clinical trial (or on request), submit a progress report to the EC's containing an overview of all SARs occurred during the reporting period and taking into account all new available safety information received during the reporting period.

10. Statistical Consideration

Sample size calculation for a validation study on artificial intelligence in polyp detection. The aim is to compare the accuracy of the detection by AI versus the endoscopist.

- The accuracy by AI is assumed to be 97% (pilot data). The accuracy by the endoscopist in the study setting of university hospitals is assumed to be 95%.
- The sample size is the number of polyps needed with an average of 2 polyps per patient (pilot data)

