As polyps are clustered within patients, we need to take into account a clustering effect. Based on pilot data the intraclass correlation (ICC) was estimated as 0.003 which can be considered as negligible. (This means that there are no patient-effects, which would mean that probabilities of detection differ between patients).

The sample size calculations below are performed for the number of polyps needed, assuming independence.

- A sample size calculation was performed for a McNemar test for paired proportions.
- Sensitivity is assumed to be >90% (pilot data)
- Power = 90%
- A 5% two-sided significance level a difference in accuracy between AI and endoscopist, assuming respectively 97% and 95% of accuracy
- Indicating a total number of 2084 polyps is needed to prove superiority.

Statistical analyses will be performed according to the accuracy and extra detections. Descriptive statistics will be used for continuous variables and expressed as mean, median and range values. Association BBPS, ADR and location will be examined through logistic regression method, ROC curves, sensitivity and specificity.

11. Informed Consent

Written consent documents will embody the elements of informed consent as described in the Declaration of Helsinki and the ICH Guidelines for GCP and will be in accordance with all applicable laws and regulations. The informed consent form describes the planned and permitted uses, transfers, and disclosures of the subject's personal and personal health information for purposes of conducting the study. The informed consent form further explains the nature of the study, its objectives, and potential risks and benefits, as well as the date informed consent is given. The informed consent form will detail the requirements of the participant and the fact that he or she is free to withdraw at any time without giving a reason and without prejudice to his or her further medical care.

The investigator is responsible for the preparation, content, and IRB or IEC approval of the informed consent form and if applicable, the subject authorization form. The informed consent form must be approved by both the IRB or IEC and the sponsor prior to use.

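### Exploratory endpoint 2 relates ADR to a raw count of AI false negatives, which can rise with the endoscopist's polyp yield even if the AI's miss probability is constant

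*Combined protocol and SAP*

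**What the plan says.** All references are to the combined protocol and SAP.

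- Section 5, exploratory endpoint 2: "Correlation between the endoscopist's historical adenoma detection rate and the number of extra detections and false negative detections by the artificial intelligence system". Both outcomes are numbers. No denominator or offset is given.
- Section 4 defines the AI false negative as "Every polyp that is found by the endoscopist and is not detected by the AI tool before the attempt of endoscopic optical diagnosis".
- Section 8: "A single pass withdrawal will be applied during inspection". There is no second, independent examination, so a polyp missed by both endoscopist and AI is never counted.
- Section 6 admits endoscopists with ADR above 20% and below 50%.
- Section 10 has one sentence on the analysis of ADR: "Association BBPS, ADR and location will be examined through logistic regression method, ROC curves, sensitivity and specificity". It does not say what the outcome is, whether the unit is the polyp, the patient or the endoscopist, or which polyps enter.

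**The concern.** A false negative needs an opportunity, and the only opportunity the plan recognises is a polyp the endoscopist has found. The expected count is the number of such polyps times the AI's miss probability. ADR is itself a measure of how much an endoscopist finds, so it may well move the first factor. A positive association between ADR and the count then cannot separate an AI that performs worse from an AI that was shown more polyps. Totals per endoscopist also grow with the number of procedures each one contributes, which the plan does not fix.

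This endpoint is where the plan asks whether the AI's failures and added detections vary with endoscopist performance. A reader could take an artefact of yield as evidence that the AI fails more often with better endoscopists.

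**Working it through.** **The plan's own figure.** Exploratory endpoint 2 has none. The only sample-size figure is 2084 polyps for the McNemar comparison of 97% with 95% at two-sided 5% and 90% power (section 10). If AI and endoscopist detections are taken as independent (an assumption), the discordant probabilities are 0.97 × 0.05 = 0.0485 and 0.03 × 0.95 = 0.0285. Exact power at 2084 is then 89.95%. The figure reproduces, and nothing below changes it.

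**Inputs from the documents.** AI accuracy 97% (section 10), used here as a constant miss probability m = 1 − 0.97 = 0.03. Endoscopist accuracy 95% (section 10). Cited polyp miss rate as high as 21% (section 2), so a low sensitivity of 0.79. ADR 20% to 50% (section 6). 2084 polyps at 2 per patient, so 2084/2 = 1042 colonoscopies.

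**Assumed, because the documents are silent.** 10, 20 or 30 endoscopists with equal volumes; ADR uniform over 20% to 50%; the way polyps found scale with ADR; an average of 1.9 found polyps per colonoscopy (0.95 × 2) where yield depends on ADR; 2.1 polyps present per patient where only sensitivity varies.

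**Step 1: expected counts.** Expected false negatives = polyps found × m.
- ADR acts only through sensitivity p: 2.1 × 0.79 × 0.03 = 4.98 per 100 patients, and 2.1 × 0.95 × 0.03 = 5.98 per 100. The ratio is 0.95/0.79 = 1.20.
- Yield rises with the square root of ADR: ratio across the range √(50/20) = 1.58.
- Yield proportional to ADR: ratio 50/20 = 2.5.

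The AI is identical in all three.

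**Step 2: what a correlation across endoscopists would show.** Polyps found were simulated as Poisson and false negatives as Binomial(found, 0.03). Historical ADR was correlated (Pearson) with the count.

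| Assumed link of yield to ADR | Mean r (10 to 30 endoscopists) | Trials with p < 0.05 |
|---|---|---|
| None | about 0 | 4-6% |
| Sensitivity 0.79 to 0.95 | 0.12 to 0.08 | 6-7% |
| Square root | 0.28 to 0.17 | 13-16% |
| Proportional | 0.50 to 0.32 | 34-42% |

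Repeat runs differ by a few percentage points. With false negatives divided by endoscopist-found polyps, mean r is about 0 and the rejection rate about nominal in every row.

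**Step 3: does logistic regression cure it?** That depends on the unit and risk set.
- Per patient, outcome any false negative: 1 − exp(−0.03 × polyps found) gives 3.0%, 5.8% and 8.6% at a mean of 1, 2 and 3 found polyps (Poisson assumed). The artefact stays.
- Per polyp, among all polyps detected by either: p × m / [1 − (1 − p) × m] gives 0.0237/0.9937 = 2.4% at p = 0.79 and 0.0285/0.9985 = 2.85% at p = 0.95. A residue stays.
- Per polyp, among endoscopist-found polyps: p × m / p = 3.0% at every p. The artefact goes.

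**Step 4: the extra-detection half.** Expected extra detections = polyps present × (1 − p) × 0.97. With 2.1 present this is 42.8 per 100 patients at p = 0.79 and 10.2 at p = 0.95. That fall is partly the effect of interest. The count nevertheless still scales with polyp burden and volume. Dividing by AI-detected polyps (2.1 × 0.97 = 2.037 per patient) gives 0.428/2.037 = 0.21 and 0.102/2.037 = 0.05, which is the endoscopist's miss proportion.

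**The case against.** The strongest reply is that the raw-count reading is too literal. Exploratory endpoints 3 and 4 use similar wording for polyp size and Paris class, which belong to single polyps. The sample size is counted in polyps, and the method section 10 names for ADR needs a binary outcome. On that view, number is loose wording for false-negative status per polyp. This stands in part: the plan does not commit to a Pearson correlation of counts per endoscopist, and a reader should not infer that a biased analysis has been chosen. But a per-patient logistic model fits the section 10 sentence equally well and keeps the artefact, so the sentence does not settle the matter.

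Second, the size is driven by assumption. This stands. The documents do not say how historical ADR relates to all polyps found per study colonoscopy, and the scenario built on their own detection figures gives an error rate barely above 5%.

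Third, the simulated success of the proportion is circular, because false negatives were generated as a fixed share of found polyps. This also stands. If higher-ADR endoscopists find subtler polyps, the proportion could still rise with ADR through case mix, so the denominator alone is not a full remedy.

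Fourth, the endpoint is one of six exploratory ones, with no hypothesis or decision attached. That limits the weight of the point but does not remove it.

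**Conclusion.** The point holds in a limited form. From the plan's own definition, the number of AI false negatives rises with the endoscopist's yield at a constant AI miss probability, and no stated rule in section 10 prevents that rise from being read as an ADR effect. The direction rests on one assumption, that found polyps increase with ADR. The size cannot be taken from the documents: the scenarios run from a rejection rate of about 6-7% to about 34-42% against a nominal 5%, and none is an estimate for this trial.

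Three stronger readings are tempting and are not supported. A large spurious correlation is not established, since it needs yield to scale steeply with ADR. The endpoint does not compare the two counts with each other; it names two outcomes in one sentence. And the primary and secondary endpoints and the 2084-polyp calculation are not touched. This is a worthwhile, inexpensive correction to one exploratory endpoint.

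**What to change.** In section 5, restate exploratory endpoint 2 as two proportions, each on its own risk set: (a) AI false negatives among endoscopist-found polyps, and (b) AI-only polyps among all AI-detected polyps (those found by both plus those found by the AI alone).

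In section 10, state that each is analysed by polyp-level logistic regression on historical ADR with clustering by endoscopist and by patient. Add a sensitivity analysis adjusting for polyp size and Paris class, both already part of the optical assessment in section 8. Do not correlate ADR with raw or per-colonoscopy counts.

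In section 8, add each endoscopist's historical ADR as a recorded study variable. The performing endoscopist is listed there, but the ADR value is not.

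The cost is a few sentences and one value per endoscopist, with no extra patients or procedures. The small downside is wider intervals, because the endoscopist is the effective unit for ADR.

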When a detection is made by the AI system and this detection can clearly be categorized the endoscopist and second observer do not communicate. In case of a detection of the AI-system that was not seen by the endoscopist or is unclear to the second observer, the second observer will ask to re-evaluate the indicated region to determine whether after second look it is a true positive not detected by the endoscopist or a clinically relevant false positive detection of the AI system since it caused the endoscopist to take an extra action. Endoscopists will inspect perform a standard colonoscopy with a single withdrawal, inspecting each segment only once, except when the second observer asks to reinspect a certain area in case of a clinically relevant AI detection. The different timings in each segment will be separately measured with a built-in chronometer in the artificial intelligence tool. Time measurement will be initiated once withdrawal is initiated in the caecum and will be determined for every specific segment. In case of therapeutic actions, time registration will be paused and restarted after completion of this therapeutic act. Automated time calculation is integrated in the AI system and provides an overview of the real withdrawal time and the performed therapeutic time. The entire procedure is recorded. The practical set-up is shown in figure 2.

[figure not shown]

Figure 2: Basic set-up of the computer-aided diagnostic (CAD) tool as second observer during endoscopy. A patient undergoes a diagnostic colonoscopy performed by an experienced endoscopist (ADR > 20% and <50%), while a second observer watches the by the CAD-analyzed video to count and categorize the indicated detections. There is no communication between the endoscopist and the second observer unless a clinically relevant finding is found by the second observer or a polyp or clinically relevant finding is made by the endoscopists.

7. Study Population

Inclusion criteria

- Age ≥40 years
- Referral for screening, surveillance or diagnostic colonoscopy
- Able to give informed consent by the patient or by a legal representative

Exclusion criteria for study inclusion

- <40 years old
- Referral for a therapeutic colonoscopy
- Known Lynch syndrome or FAP syndrome
- Any contraindication for colonoscopy or biopsies of the colon

- Uncontrolled coagulopathy
- Confirmed diagnosis of inflammatory bowel disease prior to the scheduled colonoscopy
- Short bowel or ileostomy
- Pregnancy

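### Exploratory endpoint 5 correlates a part with its whole: if additional detections count in the total, r is positive even when polyp burden has no effect on the chance of a miss

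*Combined protocol and SAP*

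**What the plan says.** Section 5, exploratory endpoint 5, is one line: "Correlation between the total number of polyps per colonoscopy and additional detections". It attaches a unit, the colonoscopy, to the total. It gives no unit for the additional detections (count, yes/no per polyp, or proportion), no coefficient or model, and no statement that the additional detections are inside or outside the total.

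Other places bear on it:

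- Section 4 counts as a true positive a lesion that the endoscopist first missed and that is diagnosed as a polyp on closer inspection. Section 6 calls the same event "a true positive not detected by the endoscopist".
- Secondary endpoint 4 builds on this event: "polyp miss rate defined as the additional detection of polyps during colonoscopy". Secondary endpoints 2 and 3 use it as a plain count of extra polyps.
- Section 8 limits which polyps are in the study: "Any additional apparent hyperplastic polyps in the rectosigmoid exceeding the number of 5 will be discarded from the study for practical reasons".
- Section 10 has one sentence on associations: "Association BBPS, ADR and location will be examined through logistic regression method, ROC curves, sensitivity and specificity". Polyp count is not in it.
- Section 10 assumes 2 polyps per patient on average, 95% accuracy for the endoscopist, and an intraclass correlation of 0.003, which it treats as no patient effect on detection.

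**The concern.** A correlation is normally tested against zero, and zero is read as no relation. Here zero is not the value expected when polyp burden has no effect on missing. A colonoscopy with six polyps offers six chances of an additional detection, and one with a single polyp offers one. Additional detections therefore rise with the total even if every polyp is equally likely to be missed, and that equal-chance case is section 10's own working assumption.

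At stake is the meaning of one exploratory result. A positive, highly significant r could be published although the miss probability is flat, or even lower in patients with many polyps.

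**Working it through.** **Inputs.** Endpoint 5 has no figure of its own to reproduce. From section 10: 2084 polyps / 2 per patient = 1042 patients, with a mean of 2 polyps. Assumptions:

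- The miss probability p is 5%, taken as 1 minus the stated 95% accuracy; 2% is shown as well.
- The AI flags every missed polyp.
- The spread of polyp counts, which the protocol does not give, is represented by three distributions with mean 2: 1+Poisson (variance 1), Poisson (variance 2) and negative binomial of size 1 (variance 6).

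**Total includes the additional detections.** Let T be the total and A the additional detections, with A given T binomial(T, p). Then

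Cov(A,T) = p·Var(T), Var(A) = p(1-p)·E(T) + p²·Var(T), and so r = √[ p·Var(T) / ((1-p)·E(T) + p·Var(T)) ].

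At p = 0.05:

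- variance 1: √(0.05/1.95) = 0.16
- variance 2: √(0.10/2.00) = 0.22
- variance 6: √(0.30/2.20) = 0.37

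At p = 0.02 the values are 0.10, 0.14 and 0.24. With 1042 patients an r of about 0.06 already reaches p<0.05 (1.962/√1042 = 0.061). Leaving out polyp-free colonoscopies, where no additional detection is possible, gives 0.16, 0.19 and 0.31 at 5% miss.

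**Total excludes the additional detections.** Cov(A, T-A) = p(1-p)·(Var(T) - E(T)). At p = 0.05, r = -0.15, 0.00 and +0.24. The miss probability is the same in all three cases; only the spread of counts sets the sign.

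**Simulation** (5000 trials of 1042 patients, total including additional detections). In the falling scenario the miss probability is 8% at 1 polyp, 5% at 2-3 and 3% at 4 or more; this gradient is chosen for illustration.

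| Miss probability | Result | 1+Poisson | Poisson | Neg. binomial |
|---|---|---|---|---|
| constant 5% | r has p<0.05 | 99.7% | 100% | 100% |
| constant 2% | r has p<0.05 | 87% | 99% | 100% |
| falling | mean r | 0.07 | 0.13 | 0.24 |
| falling | r significantly positive | 64% | 99% | 100% |
| falling, patients with polyps only | r significantly positive | 64% | 63% | 96% |

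**Alternative on the same data.** This is a logistic model per polyp: additional detection yes/no, on the number of other polyps in that colonoscopy (T-1), with standard errors clustered by patient. Under a constant miss of 2% to 10% it rejects in 5.1% to 6.7% of trials. In the falling scenario the median odds ratio per extra polyp is 0.77, 0.79 and 0.91. It is significantly below 1 in 76%, 80% and 60% of trials and significantly above 1 in none.

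**The case against.** The best answer is that nothing here is wrong as long as the endpoint is about yield. Secondary endpoints 2 and 3 are counts, exploratory endpoints 1 to 4 also speak of numbers of detections, and extra polyps found per colonoscopy is a quantity worth reporting. That stands, and the fix keeps it.

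Several stronger readings are tempting, and the documents do not support them:

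- *The sponsor will present a positive r as a higher relative miss.* The protocol nowhere says how r will be interpreted.
- *The expected r is positive whatever the total means.* This is guaranteed only if the total includes the additional detections. That is the natural reading but it is not stated, and section 4 also counts as true positives lesions biopsied in case of doubt, which may not all enter a polyp total.
- *The unit is wholly undefined.* The line gives the colonoscopy as the unit for one of the two variables. A per-polyp analysis is not excluded either: exploratory endpoints 3 and 4 concern attributes of single polyps.
- *The rectosigmoid polyps beyond five are left open.* Section 8 largely settles that they are outside the study; the total only needs to say so.
- *The correlation carries no information on missing.* It does respond. With miss equal to 10% divided by the polyp count, r falls to 0.00, 0.07 and 0.11 under the three spreads, and to 0.00 among patients with polyps. The trouble is that r = 0 then marks a steeply falling miss probability, not an unchanged one.

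It is also fair that 5% is inferred from an accuracy figure rather than stated as a miss rate. The conclusion does not hang on it, since the 2% results point the same way.

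**Conclusion.** The point holds in a limited form. If the total includes the additional detections, endpoint 5 is a part-whole correlation whose expected value is positive under a constant miss probability: about 0.16 to 0.37 at 5% miss, and significant in at least 99.7% of simulated trials. If it excludes them, the sign depends on the spread of counts. On either definition a test of r = 0 cannot show whether the relative miss changes with polyp burden; on the natural reading r describes absolute yield.

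The sizes rest on the assumed 5% (or 2%) miss and the assumed spreads. The positive sign needs only that the total includes the additional detections, that the miss probability is constant and that counts vary. Severity is minor: this is one of six exploratory endpoints, and neither the primary comparison nor the 2084 polyps is touched.

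**What to change.** Add to section 10:

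1. The total is all study polyps in the colonoscopy, additional detections included, after the section 8 exclusion of excess rectosigmoid polyps.
2. The count of additional detections by number of polyps is reported descriptively, as yield per colonoscopy, without a test of r = 0.
3. Relative miss is analysed per polyp by logistic regression of additional detection (yes/no) on the number of other polyps in that colonoscopy, with standard errors clustered by patient.

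Removing the additional detections from the total is not a substitute, as the second calculation shows.

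The cost is a few sentences and one more exploratory model; no new data are needed. Yield is then shown but not tested. Precision is modest: 2084 × 5% gives about 104 events, with a 95% confidence interval for the odds ratio per extra polyp of roughly times or divided by 1.06 to 1.20, depending on the spread of counts. At 2% miss there are about 42 events, and the factor is 1.10 to 1.33.

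### Section 6 does not define when an AI detection counts as unseen by the endoscopist, so a prompted polyp the endoscopist had seen or was about to call can be scored as an endoscopist miss

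*Combined protocol and SAP*

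**What the plan says.** Section 6 gives two triggers for a prompt: "In case of a detection of the AI-system that was not seen by the endoscopist or is unclear to the second observer". The observer then asks for the area to be looked at again, "to determine whether after second look it is a true positive not detected by the endoscopist or a clinically relevant false positive detection". No third outcome is listed.

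Section 4 overlaps with this. Under clinically relevant false positives it says: "In case this is not spotted by the endoscopists, the second observer will ask the endoscopists to perform a second or close-by inspection". Its definition of a true positive has two branches: lesions diagnosed at first sight, credited to the endoscopist, and lesions diagnosed on a second or close look, on condition that the endoscopist had missed them at first. It does not say how that condition is established. A box that cannot be found again is classed as a clinically relevant false positive.

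The one explicit timing rule concerns the AI. After the endoscopist's standard verbal question, the observer presses a button that opens a 1-second window. A polyp not boxed within it is an AI false negative.

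Section 10 sizes the study on accuracies of 97% (AI) and 95% (endoscopist): "A sample size calculation was performed for a McNemar test for paired proportions".

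**The concern.** The only specified sign that the endoscopist has detected a polyp is the verbal question. Until it is spoken, the observer cannot reliably tell a miss from a lesion that the endoscopist has noticed and is approaching. Neither section sets a waiting time, requires the boxed area to have left the view, or requires the endoscopist to have moved on. The trigger for unclear detections is looser still, because it depends on the observer's uncertainty and not on what the endoscopist saw.

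Both triggers lead to the same two outcomes. A confirmed polyp that the endoscopist had seen, or would have called unaided, can therefore be recorded as an endoscopist miss. After the prompt, unaided detection of that polyp can no longer be observed directly.

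Each such error affects the primary endpoint, its histology-based counterpart (secondary endpoint 1), the counts of extra AI detections (2 and 3) and the endoscopist's miss rate (4).

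**Working it through.** **Inputs.** From section 10: 97% and 95% accuracy, 2084 polyps, two per patient on average, two-sided 5% level, 90% power, McNemar test. Clustering is set aside, as the plan does ("the intraclass correlation (ICC) was estimated as 0.003 which can be considered as negligible"); with two polyps per patient the design effect is 1 + (2 − 1) × 0.003 = 1.003. Not in the documents, so assumed: that the primary analysis is the McNemar test used for sizing, that the two readers' misses are independent, and the number of prematurely prompted polyps.

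**Step 1: the plan's figure.** Under independence the discordant cells are 0.97 × 0.05 = 0.0485 (AI only) and 0.03 × 0.95 = 0.0285 (endoscopist only). They sum to 0.077 and differ by 0.02. The asymptotic formula gives

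N = (1.96 × √0.077 + 1.2816 × √(0.077 − 0.02²))² / 0.02² ≈ 2019.

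An exact McNemar test at N = 2084 has power 0.8995 under the same assumptions, so 2084 is reproduced. The plan does not state the discordance it used.

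**Step 2: the planned signal.** 2084 × 0.02 = 41.7, a net difference of about 42 polyps in 2084 / 2 = 1042 patients.

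**Step 3: moved polyps needed to reach the threshold when the readers are equal.** Expected discordant pairs are D = 2p(1 − p) × 2084. Moving x polyps from detected by both to AI only gives an expected uncorrected statistic z = x / √(D + x).

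| True accuracy, both readers | D | x | z | Share of 2084 | One per |
|---|---|---|---|---|---|
| 97% | 121 | 24 | 24 / √145 = 1.99 | 1.2% | 1042 / 24 ≈ 43 colonoscopies |
| 95% | 198 | 30 | 30 / √228 = 1.99 | 1.4% | 1042 / 30 ≈ 35 colonoscopies |

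One polyp fewer falls short: 23 / √144 = 1.92 and 29 / √227 = 1.92. These are thresholds at expected cell counts. With sampling variation, the chance of a significant AI advantage at these counts is about 51% in both rows.

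**Step 4: chance of falsely declaring the AI superior.** Let f be the share of jointly detectable polyps (p² × 2084) prompted early and scored as endoscopist misses. Then AI only = p(1 − p) + f·p², endoscopist only = p(1 − p), and power follows from the asymptotic McNemar formula at N = 2084.

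| f | Both 97%: polyps moved | Chance | Both 95%: polyps moved | Chance |
|---|---|---|---|---|
| 0 | 0 | 2.5% | 0 | 2.5% |
| 0.5% | 9.8 | 13.5% | 9.4 | 9.6% |
| 1% | 19.6 | 38% | 18.8 | 25% |
| 2% | 39.2 | 87% | 37.6 | 69% |

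With both readers at 97%, f = 0.02 / 0.97² = 2.1% would produce the whole planned 2-point difference.

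**The case against.** Several stronger readings are tempting, and the documents do not support them.

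- *The observer may prompt at any moment.* Prompts are conditional, counting is confined to withdrawal, and the two may not communicate when a detection can clearly be categorised. Section 6 also speaks of looking again, which presupposes a first look. What remains is that section 4 allows a close look as an alternative to a second one, and a close look can be requested while the lesion is still in view.
- *Every prompted polyp becomes an endoscopist miss.* Section 4 makes the miss a condition, and section 6 refers to section 4 for the detail. A lesion already seen could be placed in the first-sight branch. But section 6 lists no such outcome and section 4 gives no test for it, so sites could score the same event differently.
- *The comparison as a whole is biased towards the AI.* Other rules can work against it: an early endoscopist call followed by the 1-second window can create an AI miss, and genuine AI-only polyps are lost when a box cannot be relocated. Only the direction of this one mechanism follows from the text.
- *The rules encourage early prompting.* Waiting does risk a relocation failure, but nothing gives the observer a stake in the result.
- *The error cannot be repaired.* The whole procedure is recorded, so video might show whether the lesion was in view or being approached. It cannot show whether it would have been called, and no adjudication of first detection is planned.
- *Moving 24 or 30 polyps makes the test significant.* It does so only about half the time.

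**Conclusion.** The point stands as a gap in the scoring rule for one side of the primary comparison, and it should be fixed. Under the rule as written, an endoscopist detection can be recorded as a miss, and an error of this kind always adds to the AI-only cell.

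The direction is established for this mechanism; the size is not, because the documents give no frequency of early prompts. The illustration of 24 to 30 polyps (1.2% to 1.4% of 2084) for roughly even odds of a false AI advantage rests on equal readers, independent misses and an uncorrected McNemar test. It shows that a small number of such errors would matter against a planned net difference of about 42. It does not show that they will occur.

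**What to change.** 1. Align sections 4 and 6. The observer asks for re-inspection only after the boxed area has left the field of view, or the endoscopist has visibly moved on without calling it. A confirmed miss is one scored under that condition.
2. Add a third outcome for prompted lesions the endoscopist had already seen, scored as detected by both. It should rest on something observable before the prompt, since a statement made afterwards is not independent of it.
3. Record on the CRF whether the lesion was still in view at the prompt and which trigger applied, and cover this in the observer training.
4. Keep polyps prompted while in view, or only because the detection was unclear, in the main comparison, flagged and scored as AI only unless the third outcome applies. Removing them would selectively delete genuine AI-only polyps and tilt the result against the AI. Prespecify one sensitivity analysis that counts them as detected by both and one that excludes them, so that the bias is bounded.

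The cost is protocol wording, a short CRF entry and an addition to the training. The downside is that waiting may leave a few more boxed areas hard to relocate. That would raise the not-relocated count and could lose some real polyps, so the count should be reported alongside the main result.
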